## 9. APPENDICES

### Appendix 1. SUMMARY OF EFFICACY ANALYSES

**Table 4. Summary of Efficacy Analyses**

Endpoint	Estimand and Analysis Type	Population	Data Inclusion and Rules for Handling Intercurrent Events and Missing Data	Analysis Model
Time to disease flare in DB phase	Primary estimand	DBFAS	Investigational product discontinuation due to study end and end of study treatment after clinical remission are treated as non-flare and censored. Investigational product discontinuation for any other reason are treated as disease flare.	Unstratified log-rank test (primary), KM
	Estimand 1 Composite Strategy		Missing data are not imputed, assuming censoring at random.	Cox Proportional Hazard Ratio (supportive)
	Primary analysis		Investigational product discontinuation due to study end and end of study treatment after clinical remission are treated as non-flare and censored. Investigational product discontinuation for any other reason are treated as disease flare.	Tipping point analysis, unstratified log-rank test
	Primary estimand	DBFAS	Missing data will be imputed, assuming censoring not at random.	
	Estimand 1 Composite Strategy		Investigational product discontinuation for reasons other than disease flare are treated as non-flare and censored.	
	Sensitivity analysis		Missing data are not imputed, assuming censoring at random.	
	Supplementary estimand	DBFAS	Investigational product discontinuation for reasons other than disease flare are treated as non-flare and censored.	Unstratified log-rank test, KM
	Estimand 4 Hypothetical Strategy		Missing data are not imputed, assuming censoring at random.	Cox Proportional Hazard Ratio
	Supplementary analysis			

**Table 4. Summary of Efficacy Analyses**

Endpoint	Estimand and Analysis Type	Population	Data Inclusion and Rules for Handling Intercurrent Events and Missing Data	Analysis Model
	Supplementary estimand  Estimand 5 Treatment Policy Strategy  Supplementary analysis	DBFAS	All data collected including those through Week 52 post randomization from study A3921165 and flare data from study A3921145 and will be included regardless of intercurrent events.  Missing data are not imputed, assuming censoring at random.	Unstratified log-rank test, KM  Cox Proportional Hazard Ratio
	Supplementary estimand  Estimand 5 Treatment Policy Strategy  Sensitivity analysis	DBFAS	All data collected including those through Week 52 post randomization from study A3921165 and flare data from study A3921145 and will be included regardless of intercurrent events.  Missing data will be imputed, assuming censoring not at random.	Tipping point analysis, unstratified log-rank test
Time to disease flare in DB phase by subgroups: age, body weight, geographic region, formulation, OL baseline oral corticosteroids use, DB baseline oral corticosteroid use, OL baseline MTX use, prior bDMARD experience	Primary estimand  Estimand 1 Composite Strategy  Subset analysis	DBFAS	Investigational product discontinuation due to study end and end of study treatment after clinical remission are treated as non-flare and censored. Investigational product discontinuation for any other reason are treated as disease flare.  Missing data are not imputed, assuming censoring at random.	KM, Cox Proportional Hazard Ratio
Occurrence of disease flares by DB visit	Primary estimand  Estimand 1 Composite Strategy	DBFAS	Investigational product discontinuation due to study end and end of study treatment after clinical remission are treated as non-flare and censored. Investigational product	KM

**Table 4. Summary of Efficacy Analyses**

Endpoint	Estimand and Analysis Type	Population	Data Inclusion and Rules for Handling Intercurrent Events and Missing Data	Analysis Model
	Secondary analysis		discontinuation for any other reason are treated as disease flare.  Missing data are not imputed, assuming censoring at random.	
	Supplementary estimand  Estimand 4 Hypothetical Strategy  Supplementary analysis	DBFAS	Investigational product discontinuation for reasons other than disease flare are treated as non-flare and censored.  Missing data are not imputed, assuming censoring at random.	KM
	Supplementary estimand  Estimand 5 Treatment Policy Strategy  Supplementary analysis	DBFAS	All data collected including those through Week 52 post randomization from study A3921165 and flare data from study A3921145 and will be included regardless of intercurrent events.  Missing data are not imputed, assuming censoring at random.	KM
Occurrence of disease flares by DB visit by subgroups: age, body weight, geographic region, formulation, OL baseline oral corticosteroids use, DB baseline oral corticosteroid use, OL baseline MTX use, prior bDMARD experience	Primary estimand  Estimand 1 Composite Strategy  Subset analysis	DBFAS	Investigational product discontinuation due to study end and end of study treatment after clinical remission are treated as non-flare and censored. Investigational product discontinuation for any other reason are treated as disease flare.	KM

**Table 4. Summary of Efficacy Analyses**

Endpoint	Estimand and Analysis Type	Population	Data Inclusion and Rules for Handling Intercurrent Events and Missing Data	Analysis Model
			Missing data are not imputed, assuming censoring at random.	
Adapted JIA ACR responses by DB visit	Secondary estimand	DBFAS	For investigational product discontinuation due to study end and end of study treatment after clinical remission, use last ACR value before discontinuation. Investigational product discontinuation for any other reason are treated as non-response.	Normal approximation
	Estimand 2 Composite Strategy  Secondary analysis		Missing responses are treated as non-response.	
	Estimand 6 Treatment Policy Strategy  Supplementary analysis	DBFAS	The intercurrent event of investigational product discontinuation will not be considered. All the data collected while On- and Off-investigational product until Week 52 will be used to derive the endpoints.  Missing responses are treated as non-response.	Normal approximation

**Table 4. Summary of Efficacy Analyses**

Endpoint	Estimand and Analysis Type	Population	Data Inclusion and Rules for Handling Intercurrent Events and Missing Data	Analysis Model
JADAS-27 ESR inactive disease by DB visit	Secondary estimand  Estimand 2 Composite Strategy  Secondary analysis	DBFAS	For investigational product discontinuation due to study end and end of study treatment after clinical remission, use last JADAS-27 ESR value before discontinuation.  Investigational product discontinuation for any other reason are treated as active disease.  Missing responses are treated as active disease.	Normal approximation
JADAS-27 ESR minimal disease activity by DB visit	Secondary estimand  Estimand 2 Composite Strategy  Secondary analysis	DBFAS	For investigational product discontinuation due to study end and end of study treatment after clinical remission, use last JADAS-27 ESR value before discontinuation.  Investigational product discontinuation for any other reason are treated as non-response for minimal disease activity.  Missing responses are treated as non-response for minimal disease activity.	Normal approximation
JADAS-27 CRP inactive disease by DB visit	Secondary estimand  Estimand 2 Composite Strategy  Secondary analysis	DBFAS	For investigational product discontinuation due to study end and end of study treatment after clinical remission, use last JADAS-27 CRP value before discontinuation.  Investigational product discontinuation for any other reason are treated as active disease.  Missing responses are treated as active disease.	Normal approximation

**Table 4. Summary of Efficacy Analyses**

Endpoint	Estimand and Analysis Type	Population	Data Inclusion and Rules for Handling Intercurrent Events and Missing Data	Analysis Model
JADAS-27 CRP minimal disease activity by DB visit	Secondary estimand  Estimand 2 Composite Strategy  Secondary analysis	DBFAS	For investigational product discontinuation due to study end and end of study treatment after clinical remission, use last JADAS-27 CRP value before discontinuation.  Investigational product discontinuation for any other reason are treated as non-response for minimal disease activity.  Missing responses are treated as non-response for minimal disease activity.	Normal approximation
Absence of fever by DB visit	Secondary estimand  Estimand 2 Composite Strategy  Secondary analysis	DBFAS	For investigational product discontinuation due to study end and end of study treatment after clinical remission, use last oral temperature value before discontinuation.  Investigational product discontinuation for any other reason are treated as fever.  Missing responses are treated as fever.	Normal approximation
JIA ACR inactive disease by DB visit	Secondary estimand  Estimand 2 Composite Strategy  Secondary analysis	DBFAS	For investigational product discontinuation due to study end and end of study treatment after clinical remission, use last JIA ACR value before discontinuation.  Investigational product discontinuation for any other reason are treated as non-response.  Missing responses are treated as active disease.	Normal approximation
Clinical remission in DB phase	Secondary estimand	DBFAS	For investigational product discontinuation due to study end and end of study treatment after clinical remission, use last clinical	Normal approximation

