8.1.2. Fever and Absence of Fever Assessment

At each study visit, the subject’s oral temperature will be taken. From Day 7 onward, the subject will also be asked if they had fever, defined as temperature $>38^{\circ}\text{ C}$ (100.4° F), due to sJIA, in the last 7 days before the visit. “Absence of fever”, defined as the documented absence of fever due to sJIA in the week preceding the assessment, will be evaluated at every visit from the Day 7 visit onward, as a key component of the Adapted JIA ACR response.

Subjects will be provided with a thermometer to measure their oral temperature on days that have fever symptoms. Each subject will receive a diary at Screening to record their temperature. The parent/legal guardian should complete the diary or supervise the completion of the diary by the subject. If subjects have a fever, the temperature should be recorded twice daily (in the morning and evening); the highest temperature since previous diary recording should be reported in the diary. Subjects will return the diary to the clinic at each study visit.

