#### 2.3.2.1. Binary Secondary Endpoints in Double-Blind Phase

For binary endpoints such as adapted JIA ACR 30/50/70/90/100 response at each double-blind phase visit, the estimand also uses composite strategy (Estimand 2) and includes the following 5 attributes:

- Population: sJIA patients, as defined by the inclusion criteria for the double-blind phase, who are randomized.
- Treatment: tofacitinib 5 mg BID, placebo

- Variable: binary endpoints such as aJIA ACR 30/50/70/90/100 response at each double-blind phase visit through Week 52.

Patients who complete study participation after maintaining JIA ACR inactive disease for at least 24 weeks (clinical remission) in the double-blind phase, and patients who are still active in the double-blind withdrawal phase of the study but have to discontinue before Week 52 due to study end, will use the last on-treatment windowed visit ([Appendix 3.13](#)) ACR value (ie, last observation carried forward (LOCF)), from that visit onward until Week 52 visit.

Patients who discontinue from the investigational product for any other reasons before Week 52 are considered as treatment failure, ie, ACR non-responders, from that visit onward until Week 52 visit. If there is an on-treatment ACR assessment that falls within the same windowed visit with the investigational product discontinuation, the ACR assessment will prevail.

- Intercurrent event: investigational product discontinuation will be the intercurrent event. The intercurrent event is captured through the variable definition. Data collected after discontinuation of the investigational product (ie, off-treatment data) will not be included to derive the endpoint, ie, only on-treatment data ([Appendix 3.13](#)) collected prior to or at Week 52 visit will be used.
- Population-level summary: difference in proportion of subjects achieving binary endpoint response such as aJIA ACR 30/50/70/90/100 response at each double-blind phase visit through Week 52 between those assigned to tofacitinib at randomization versus those assigned to placebo at randomization.

Estimands for all other binary secondary endpoints except occurrence of disease flares in double-blind phase will follow the same composite strategy as the above secondary estimand. See endpoint definitions in [Section 3.2.1](#) and [Appendix 1](#) and missing data handling in [Section 5.3](#) for specific differences.

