### **3.2. Secondary Efficacy Endpoints**

#### **3.2.1. Double-blind Randomized Withdrawal Phase**

- Occurrence of disease flares in the double-blind phase at each visit.
- Adapted JIA ACR 30/50/70/90/100 response at every visit in the double-blind phase, with individual component improvements calculated relative to the open-label baseline.
- “Absence of fever”, defined as absence of fever (fever defined as oral temperature  $>38^{\circ}\text{C}/100.4^{\circ}\text{F}$ ) due to sJIA in the week preceding the assessment at every visit in the double-blind phase.
- Change from DB baseline in Juvenile Arthritis Disease Activity Score (JADAS-27, calculated based on the ESR and CRP inflammation biomarkers separately) at every visit in the double-blind phase.
- Change from baseline (both open-label and double-blind baseline) in each sJIA ACR core variable (i.e., number of joints with active arthritis, number of joints with limited range of motion, physician global evaluation of disease activity, parent/legal guardian/subject evaluation of overall well-being (from the CHAQ), disability index from the CHAQ, and ESR) at every visit in the double-blind phase.
- Occurrence of inactive disease status and minimal disease activity (JADAS-27, calculated based on the ESR and CRP inflammation biomarkers separately) at every visit in the double-blind phase. Refer to [Appendix 3.6](#) for detailed definitions.
- Occurrence of JIA ACR inactive disease status at every visit in the double-blind phase. Refer to [Appendix 3.7](#) for detailed definitions.
- Clinical remission (24 weeks consecutive JIA ACR inactive disease, starting from double-blind phase day 1) in the double-blind phase.
- Change from DB baseline in Child Health Questionnaire (CHQ) responses every 6 months thereafter in the double-blind phase.
- Change from DB baseline in Child Health Assessment Questionnaire (CHAQ) - Discomfort Index at every visit in the double-blind phase.

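### SAP Table 4 carries forward a last oral temperature for absence of fever, which is not the endpoint as defined (no sJIA fever in the preceding week); a minor wording error that can misclassify a few carried-forward visits

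*SAP*

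**What the plan says.** SAP 3.2.1 defines absence of fever in the double-blind phase as no fever (oral temperature above 38 C) "due to sJIA in the week preceding the assessment at every visit in the double-blind phase". Protocol 8.1.2 says the same: "documented absence of fever due to sJIA in the week preceding the assessment". That section treats the visit temperature and the weekly question as two items: "oral temperature will be taken. From Day 7 onward, the subject will also be asked if they had fever". Protocol 6.7 has the absence-of-fever status evaluated at each double-blind visit, with the temperature diary reviewed, and recorded in the eCRF.

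For intercurrent events, SAP 2.3.2.1 (Estimand 2) takes the last on-treatment windowed-visit value for children who finish after clinical remission or who are still active when the study ends before their Week 52: "ie, last observation carried forward (LOCF)), from that visit onward until Week 52 visit". It is written for the ACR response and then extended: "Estimands for all other binary secondary endpoints except occurrence of disease flares in double-blind phase will follow the same composite strategy". The section sends the reader to SAP 3.2.1, Appendix 1 and SAP 5.3 for differences between endpoints.

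In Appendix 1, Table 4, the row for absence of fever says, for those two exit groups, "use last oral temperature value before discontinuation". For everyone else, "Investigational product discontinuation for any other reason are treated as fever", and missing responses are also scored as fever.

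**The concern.** The endpoint has two qualifiers that a temperature does not have: the fever must be attributed to sJIA, and the look-back is a week. A carry-forward rule built on the last temperature drops both. A child with an intercurrent infection at the last visit could be carried to Week 52 as having fever. A child with a day of sJIA fever earlier in the final week could be carried forward as fever-free.

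SAP 6.2.1.1 presents a confidence interval and a p-value for this endpoint at each scheduled visit through Week 52, so any such error enters the reported treatment differences. It could also produce contradictory records. Adapted ACR response (SAP Appendix 3.4) and inactive disease (Appendix 3.7) both turn on fever due to sJIA. A remission completer with a viral fever at the last visit could therefore be carried forward as a responder with inactive disease and, on the fever endpoint, as having fever.

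**Working it through.** There is no stated figure to reproduce. The check has three parts.

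**1. Is the Table 4 cell operative?** SAP 2.3.2.1 names Appendix 1 as a place where endpoints differ. SAP 5.3.2 gives only the general missing-as-non-response rule and refers back to the estimand. SAP 5.3.2.1 to 5.3.2.3 cover ACR response, JADAS, and inactive disease with remission; none covers fever. The Table 4 cell is therefore the only fever-specific carry-forward instruction.

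**2. Where do the literal rule and the definition disagree?** All possible combinations at the last visit used:

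| Last temperature | That reading due to sJIA | sJIA fever in preceding week | Literal rule | Definition |
|---|---|---|---|---|
| 38 C or below | – | no | absent | absent |
| 38 C or below | – | yes | absent | **fever** |
| above 38 C | no | no | fever | **absent** |
| above 38 C | no | yes | fever | fever |
| above 38 C | yes | yes | fever | fever |

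Two rows disagree.

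- *Case (a), row 3.* A non-sJIA fever at the last reading is scored as fever. This can happen in either exit group.
- *Case (b), row 2.* A normal last reading after sJIA fever earlier that week is scored as fever-free. It should not arise in remission completers, because inactive disease excludes fever attributable to sJIA (SAP Appendix 3.7) and remission is 24 continuous weeks of inactive disease. In children active at study end it is essentially limited to isolated or non-consecutive fever days: sJIA fever on two or more consecutive days is a flare (Appendix 3.3), and a child who flares is not in a carry-forward group.

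**3. How many visits, and how large a shift per child?** Visits every 4 weeks from Week 4 to Week 52 number 52/4 = 13.

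- Last on-treatment visit at Week 24, the earliest remission: Weeks 28 to 52 are filled, (52 − 24)/4 = 7 visits. Only case (a) applies to such a child.
- Active at study end and last seen at Week 4, the extreme: Weeks 8 to 52 are filled, (52 − 4)/4 = 12 visits.
- Protocol 10.1.1 plans 54 randomized at 1:1, so 54/2 = 27 per arm. One misclassified child shifts that arm's rate by 1/27 = 3.7 percentage points at each filled visit.

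The last figure is what a single misclassification does to any binary endpoint in arms of this size. It is not an estimate of the effect, because neither document gives a rate of infection fever or of isolated sJIA fever.

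**The case against.** The best defence is that the cell is shorthand. Table 4 is a summary, and neighbouring rows also name an input: the last ACR value or the last JADAS-27 value. SAP 3.2.1 itself defines fever by oral temperature, and nothing says the attribution and the week are dropped. The cell does not say clinic reading either; diary readings taken at home are also oral temperatures. This may well be what the authors meant.

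It does not fully rescue the wording. A JADAS-27 score determines its binary endpoints through fixed cut-offs (SAP Appendix 3.6), so carrying the score carries the endpoint. No single temperature, from clinic or diary, determines the cause or the week's status. The clinical-remission row carries forward a status, so the table can say status where that is meant.

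Two stronger readings are tempting, and the documents do not support them. A reader might infer that any fever-free last reading is scored wrongly from then on; it is wrong only if sJIA fever occurred in that same week. A reader might also infer that the by-visit differences and p-values as a whole belong to another endpoint. Observed visits follow the SAP 3.2.1 definition. Only carried-forward visits in two exit groups, through Week 52, can differ, and only in cases (a) and (b).

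**Conclusion.** The cell is wrong as written, and the matter is minor. It names a variable that is not the defined endpoint, in the only place that gives a fever-specific carry-forward instruction. Few children are likely to be affected, and the frequency cannot be derived from the documents. The primary endpoint, the flare count and the power do not depend on this rule.

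The conclusion assumes that a programmer follows the cell literally. If it is read through SAP 3.2.1, no misclassification occurs and only the wording needs correcting. The per-child shift of about 3.7 points assumes that the planned 54 children are randomized evenly.

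**What to change.** In SAP Appendix 1, Table 4, in the row for absence of fever by double-blind visit, replace the last oral temperature with the last on-treatment windowed-visit absence-of-fever status (no fever due to sJIA in the preceding week). This agrees with SAP 2.3.2.1 and 3.2.1. The rules for other discontinuations and for missing responses can stay as they are.

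The cost is a few words in one cell. The status is already recorded at every double-blind visit, so no new data are needed. The change should be made before unblinding.

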**Table 4. Summary of Efficacy Analyses**

Endpoint	Estimand and Analysis Type	Population	Data Inclusion and Rules for Handling Intercurrent Events and Missing Data	Analysis Model
	Estimand 2 Composite Strategy  Secondary analysis		remission status before discontinuation. Investigational product discontinuation for any other reason are treated as non-response for active disease.  Missing responses are treated as active disease.	
ACR 30/50/70 response and JIA ACR inactive disease by DB visit and by subgroups: age, body weight, geographic region, formulation, OL baseline oral corticosteroids use, DB baseline oral corticosteroid use, OL baseline MTX use, prior bDMARD experience	Secondary estimand  Estimand 2 Composite Strategy  Subset analysis	DBFAS	For investigational product discontinuation due to study end and end of study treatment after clinical remission, use last JIA ACR value before discontinuation. Investigational product discontinuation for any other reason are treated as non-response/active disease.  Missing responses are treated as non-response/active disease.	Normal approximation
JADAS-27 ESR scores change from DB baseline by DB visit	Estimand 7 Hypothetical Strategy  Secondary analysis	DBFAS	Only data collected On-investigational product are included.  Missing data are not imputed and handled using MMRM.	MMRM with terms treatment, visit, treatment*visit, DB baseline, DB baseline*visit
JADAS-27 CRP scores change from DB baseline by DB visit	Estimand 7 Hypothetical Strategy  Secondary analysis	DBFAS	Only data collected On-investigational product are included.  Missing data are not imputed and handled using MMRM.	MMRM with terms treatment, visit, treatment*visit, DB baseline, DB baseline*visit

